## **2 Device Use and Description**

### **2.1 Device Description and Device Use**

Study devices are manufactured by Boston Scientific Corporation. The AXIOS™ Stent is a flexible, fully-covered self-expanding metal stent that is preloaded within the Electrocautery-Enhanced Delivery System. The stent is made of Nitinol and fully-covered with silicone. The AXIOS™ Stent and Electrocautery-Enhanced Delivery System is compatible with therapeutic echoendoscopes having a working channel of 3.7mm diameter or larger.

Current cleared indication for use: The AXIOS™ Stent and Electrocautery Enhanced Delivery System is cleared in the U.S. “for use to facilitate transgastric or transduodenal endoscopic drainage of symptomatic pancreatic pseudocysts  $\geq$  6cm in size and walled-off necrosis  $\geq$  6cm in size with  $\geq$  70% fluid content that are adherent to the gastric or bowel wall. Once placed, the AXIOS™ Stent functions as an access port allowing passage of standard and therapeutic endoscopes to facilitate debridement, irrigation and cystoscopy. The stent is intended for implantation up to 60 days and should be removed upon confirmation of pseudocyst or walled-off necrosis resolution.” Outside the U.S., the AXIOS™ Stent and Electrocautery Enhanced Delivery System is indicated for use to facilitate transgastric or transduodenal endoscopic drainage of a pancreatic pseudocyst or walled-off necrosis with  $\geq$  70% fluid content or to facilitate drainage of the biliary tract.

Proposed expanded indication for this IDE study: The AXIOS™ Stent and Electrocautery Enhanced Delivery System is intended “for use to facilitate transgastric or transduodenal endoscopic drainage of symptomatic pancreatic pseudocysts  $\geq$  6cm in size and walled-off necrosis  $\geq$  6cm in size that are adherent to the gastric or bowel wall. Once placed, the AXIOS™ Stent functions as an access port allowing passage of standard and therapeutic endoscopes to facilitate debridement, irrigation and cystoscopy.”

The study device is not approved for drainage of WONs with greater than 30% necrotic material and will be considered investigational for this indication. Local Institutional Review Board (IRB)/ Ethics Committee (EC) approval will be obtained at each participating center.

Study devices are labeled on the box and inner pouch and include information not limited to name of legal manufacturer, device name and dimensions, lot number, expiration date and investigational use statement. Device labeling will be provided in local language(s) as per national regulations. Devices will be available in the following matrix:

**Table 2.0-1: Device Matrix**

Description	Stent Size			Delivery System Outer Diam.
	Lumen Diameter	Saddle Length	Flange Diameter	
Electrocautery Enhanced AXIOS™ System with 10x10 Stent	10 mm	10 mm	21 mm	10.8Fr
Electrocautery Enhanced AXIOS™ System with 15x10 Stent	15 mm	10 mm	24 mm	10.8Fr
Electrocautery Enhanced AXIOS™ System with 20x10 Stent	20 mm	10 mm	29 mm	10.8Fr

For a detailed description of the AXIOS™ Stent and Electrocautery-Enhanced Delivery System, please reference the Investigator’s Brochure.

### **3 Study Objective**

To demonstrate safety and effectiveness of lumen-apposing metal stents for resolution of WONs in patients with WONs with solid component >30%.

### **4 Endpoints and Study Design**

#### **4.1 Primary Effectiveness Endpoint**

Resolution of WON with endoscopic drainage defined as radiographic decrease of WON size to ≤ 3cm evaluated by CT scan or MRI.

#### **4.2 Primary Safety Endpoint**

AXIOS™ stent related or WON drainage procedure related serious adverse events.

[figure not shown]
### **4.3 Additional Endpoints**

1. Reduction of WON-related clinical symptoms.  
*Note: WON-related symptoms as defined in Inclusion Criteria #4*
2. Technical AXIOS™ stent placement success, defined as placement in desired location using endoscopic/EUS techniques per standard of practice.
3. Technical AXIOS™ stent removal success, defined as ability to remove the AXIOS™ stent using an endoscopic snare or forceps or graspers without AXIOS™ stent removal related serious adverse events.
4. Drainage procedural time: Time elapsed between initial puncture of the WON with electrocautery to endoscope retrieval.
5. Resolution of WON with or without necrosectomy by 6 months post AXIOS™ stent removal.
6. Time to WON resolution using same definition as for primary endpoint, namely:
  - Resolution of WON with endoscopic drainage defined as radiographic decrease of WON size to  $\leq 3$ cm evaluated by CT scan or MRI.
7. Recurrence of WON after initial resolution and up to 6 months post AXIOS™ stent removal.
8. Stent lumen patency, evaluated via imaging or direct visual inspection with endoscope, and defined as one or both of the following:
  - Drainage through AXIOS™ stent visualized from the stomach or bowel, and/or
  - Visual confirmation of AXIOS™ stent lumen patency
9. Fluoroscopy (time) per endoscopic procedure.
10. Incidence of new organ failure from drainage procedure to WON resolution.
11. Change in Quality of life score (SF-12 questionnaire) from baseline to stent removal and end of study

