	

○ Organ failure assessment (Marshal scoring system)

○ Current medication

○ Labs (as needed)

● Reintervention/Necrosectomy Visits when needed during AXIOS™ stent indwell:

○ Necrosectomy initiated if WON reduction in size is deemed insufficient during WON Resolution Assessment Visit. Duration of each necrosectomy session is limited to 60 minutes

○ Percutaneous drainage or additional endoscopic drainage may be needed if reduction in WON size is insufficient or in cases of continued WON related symptoms such as infection/sepsis despite necrosectomy. Choice of stent (AXIOS™ or double pigtail plastic stent(s)) for repeat endoscopic drainage procedures will be left to the discretion of the investigator. The double pigtail plastic stent(s) or new AXIOS™ stent may be placed through the tract established by the original AXIOS™ stent or in a separate location.

○ Stent lumen patency assessment

○ Adverse event/device event assessment

○ Labs (as needed)

○ Imaging (as applicable)

○ Current medication

● Stent Removal Visit - between 14 days and 60 days of stent placement:

○ Stent lumen patency assessment

○ Stent removal after evidence of clinical and radiographic (via CT or MRI) resolution of WON

 
Note: Removal of stent by 60 days is required if WON is not resolved. Patients with unsuccessful or incomplete WON resolution by 60 days will proceed to standard of care treatment outside of this protocol after removal of the AXIOS™ stent; however, the patient outcome will continue to be followed. Alternative interventions may include surgery, endoscopic drainage with double pigtail plastic stents, percutaneous catheter drainage and necrosectomy (video-assisted retroperitoneal debridement (VARD), or endoscopic transluminal debridement, or open necrosectomy).

--	--

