### Stent Placement Procedure – Office/Hospital Visit

- AXIOS™ stent placement  
*Note: Physicians will select the site of the AXIOS™ stent placement under endoscopic guidance and choose an access location that is free from necrotic debris and intervening blood vessels, where the wall between the GI tract and fluid collection is 10mm or less,*

*and where it is possible to place the AXIOS™ stent in a position such that the inner flange (inside WON) has enough space to expand.*

- Lavaging of WON under endoscopic visualization and/or placement of nasocystic drain, or a single, 7fr double pigtail plastic stent (Boston Scientific 7Fr Advanix™ Biliary Stent) through the AXIOS™ stent at the discretion of investigator
- Stent lumen patency assessment
- Adverse event assessment/device event assessment
- Current medication
- Labs (as needed)

*Note: Labs need to be repeated at this visit ONLY IF they were collected more than 3 days before the stent placement procedure.*

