**Multiple Interventions During Index Procedure:**

Once stent is placed into the WON, dilation of the AXIOS™ stent is allowed to expand the stent if needed. Dilation can be performed to the maximal diameter of the AXIOS™ stent. A single, 7 fr double pigtail plastic stent (Boston Scientific 7Fr Advanix™ Biliary Stent) may be placed through the AXIOS™ stent at the discretion of the investigator. Access to the WON with a forward viewing diagnostic or therapeutic upper gastroscope is allowed up to 20 minutes (from time of endoscopic access of the WON) to break-up large chunks of necrosis and lavage collection at the discretion of the physician.

WON Resolution Assessment - 7 days (+/- 3 days) for inpatients and 14 (+/- 5 days) days for outpatients (needed until radiographic decrease of WON size to  $\leq$  3cm) – Office/Hospital Visit:

- Cross sectional imaging (CT or MRI) to assess reduction in WON size. If reduction in size is deemed insufficient, necrosectomy will be initiated
- Documentation of clinical improvement defined as improvement of principal WON-related symptoms
- Necrosectomy (as needed)
- Adverse event assessment/device event assessment
- Organ failure assessment (Marshal scoring system)
- Current medication
- Labs (as needed)

Reintervention/Necrosectomy Visits when needed during AXIOS™ stent indwell – Office/Hospital Visit:

- Necrosectomy initiated if WON reduction in size is deemed insufficient during WON Resolution Assessment Visit. Duration of each necrosectomy session is limited to 60 minutes
- Percutaneous drainage or additional endoscopic drainage may be needed if reduction in WON size is insufficient or in cases of continued WON related symptoms such as infection/sepsis despite necrosectomy. Choice of stent (AXIOS™ or plastic double pigtail

stent(s)) for repeat endoscopic drainage procedures will be left to the discretion of the investigator. The double pigtail plastic stent(s) or new AXIOS™ stent may be placed through the tract established by the original AXIOS™ stent or in a separate location.

- Stent lumen patency assessment
- Imaging (as applicable)
- Labs (as needed)
- Adverse event assessment/device event assessment
- Current medication

Stent Removal Visit - between 14 days and 60 days (+/- 7 days) of stent placement – Office/Hospital Visit

- Stent lumen patency assessment
- Stent removal after evidence of clinical and radiographic (via CT or MRI) resolution of WON

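### Stent lumen patency can be scored on visible drainage alone, so where a 7Fr pigtail lies inside the AXIOS stent, pigtail flow can hide a blocked lumen and patency can be overstated.

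*Protocol*

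**What the plan says.** Protocol 4.3 item 8 and SAP 5.1 item 8 define stent lumen patency in the same words, and the Protocol Synopsis and SAP section 1 repeat them. Patency is "evaluated via imaging or direct visual inspection with endoscope" and "defined as one or both of the following": first, "Drainage through AXIOS™ stent visualized from the stomach or bowel, and/or"; second, "Visual confirmation of AXIOS™ stent lumen patency". No minimum amount of drainage is set.

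Protocol 6.3, on interventions during the index procedure, says that a single 7Fr double pigtail plastic stent "may be placed through the AXIOS™ stent at the discretion of the investigator". At reintervention, plastic stents "may be placed through the tract established by the original AXIOS™ stent or in a separate location" (Synopsis; also 6.3).

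The schedule in Protocol 6.1 places patency readings at stent placement, at reintervention or necrosectomy, and at stent removal. Neither document says how to score drainage when a pigtail lies inside the AXIOS stent, and neither requires a separate look at the lumen in that case.

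**The concern.** The endpoint is meant to describe the lumen of the study device. With a pigtail running through that lumen, fluid seen leaving the stent may have come through the pigtail. The first criterion can then be met while the space around the pigtail is filled with necrosis, and the second criterion, which looks at the lumen itself, is not needed.

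Any such error goes one way. It can turn an occluded stent into a patent one but not the reverse. It also depends on how often investigators choose to place a pigtail, which can differ between sites.

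Less occlusion is one of the advantages that Protocol section 1 suggests for the large lumen. Endpoint 8 is the study's own description of it, in collections with more than 30% solid content.

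**Working it through.** **The definition**

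1. Either criterion is enough (Protocol 4.3 item 8; SAP 5.1 item 8), so visible drainage alone scores patent.
2. A 7Fr pigtail may be inside the AXIOS stent from the index procedure on (Protocol 6.3), and so may be present at any of the three kinds of patency reading.
3. Protocol 7.1 counts a collection that drains to 3 cm or less with a single 7Fr stent through the AXIOS stent as a drainage success. The protocol thus already credits drainage with an in-stent pigtail to AXIOS treatment, which makes it natural to do the same in endpoint 8.
4. Nothing later would show the effect. The pigtail poolability check in Protocol 7.4 covers only the two primary endpoints. SAP 5.4 checks pooling by site only, and SAP 5.3 plans no subgroup analysis.

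**Possible size**

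The plan states no patency rate, target or precision, so there is no figure of its own to reproduce. For illustration, assuming one reading per subject:

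overstatement of patency = f × o × m

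- f: share of subjects with a pigtail inside the AXIOS stent. Not given; varied from 0 to 100%.
- o: share of those whose AXIOS lumen is blocked. Taken from Protocol Table A1 for lumen-apposing stents: 3.8% (two-arm studies) and 7.5% (one-arm studies).
- m: share of blocked lumens scored patent on pigtail flow without the lumen criterion being applied. Not given; varied from 0 to 100%.

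Results in percentage points, with the number of 40 subjects in brackets:

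| f | m | o = 3.8% | o = 7.5% |
|---|---|---|---|
| 0% | any | 0 (0) | 0 (0) |
| any | 0% | 0 (0) | 0 (0) |
| 25% | 100% | 0.95 (0.4) | 1.9 (0.75) |
| 50% | 50% | 0.95 (0.4) | 1.9 (0.75) |
| 50% | 100% | 1.9 (0.8) | 3.75 (1.5) |
| 100% | 100% | 3.8 (1.5) | 7.5 (3.0) |

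Example: 0.50 × 0.075 × 1 = 0.0375, or 3.75 points, and 40 × 0.0375 = 1.5 subjects.

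**The case against.** The strongest reply is that the misscoring is possible but not shown. The item is headed as lumen patency and names the AXIOS stent, so an assessor may leave pigtail flow out. The second criterion is always open to the assessor, and endoscopy is commonly under way when patency is read. If the pigtail is blocked as well, no drainage is seen and the first criterion fails. All of this stands, and it is why the range starts at zero. It does not remove the problem: two assessors can follow the definition and score the same stent differently, and the resulting error can only favour patency.

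A reader might infer more in four places, and the documents do not support it:

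- **That patency is certainly overstated, or that occlusion cannot be detected in pigtail users.** The numbers of pigtails, blocked lumens and masked readings are not given, and the lumen criterion can still reveal occlusion.
- **That every plastic stent placed later has the same effect.** At reintervention the text speaks of the tract of the original stent, which need not be the AXIOS lumen. Only the single 7Fr stent is expressly placed through the AXIOS stent.
- **That the pigtail's small cross-section measures the bias.** At 3 Fr to the millimetre, 7Fr is 7/3 = 2.33 mm, and (2.33/10)² = 5.4% of a 10 mm lumen. But the first criterion sets no minimum flow, so a trickle past debris would score patent without a pigtail too. The area figure does not isolate the pigtail effect.
- **That the primary endpoints or their justification are affected.** The success criteria in Protocol 7.3 rest on resolution and related serious adverse events. The occlusion argument there comes from the external meta-analysis, not from endpoint 8. The systemic-infection rule in Protocol 7.2 has its own visual test of occlusion. The note on local infection leaves occlusion undefined but does not refer to endpoint 8.

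**Conclusion.** The concern holds as a possible upward bias in one descriptive endpoint. Visible drainage alone scores patent, a pigtail may lie inside the AXIOS stent, and a natural reading of the definition lets pigtail flow stand in for an open AXIOS lumen.

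The overstatement runs from 0 to a ceiling of 3.8 to 7.5 points, about 1.5 to 3 of 40 subjects. The ceiling assumes a pigtail in every subject, complete masking, and occlusion rates from a literature review. Those rates may not carry over to collections with more than 30% solid content or to stents holding a pigtail. No point within the range can be preferred from the documents.

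The endpoint has no threshold, SAP 4.1 excludes hypothesis testing, and neither primary success criterion depends on it. The change is still worth making because the possible error is one-directional and cheap to remove.

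**What to change.** Add one sentence to Protocol 4.3 item 8 and SAP 5.1 item 8, and carry it into the Synopsis and SAP section 1. When a plastic stent or drain lies within the AXIOS stent at the time of assessment, the stent counts as patent only if the AXIOS lumen itself is visually confirmed as open (the existing second criterion). If the lumen was viewed and not confirmed open, record not patent. If it was not viewed, record not assessable, and report the number of such readings beside the rate.

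A table of patency by visit, with and without an in-stent pigtail, would be a useful descriptive addition but is optional.

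The change concerns scoring only and leaves patient care as it is. It mostly uses endoscopic views already taken. The cost is a possibly less favourable patency figure and a few not-assessable readings, for example where patency was judged from imaging or a reintervention did not include endoscopy.

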### **4.4 Study Design**

This study is a prospective, multi-center, single arm, consecutive series study. Treatment of up to 40 subjects will take place at up to 6 clinical centers. Subjects who meet all eligibility criteria will receive the AXIOS™ stent for up to 60 days stent indwell and 6 months follow-up after stent removal.

**Figure 4.4-1: WON Drainage IDE Study Design**

## **5 Subject Selection**

### **5.1 Inclusion Criteria**

Subjects who meet all of the following criteria may be given consideration for inclusion in this clinical investigation, provided no exclusion criteria is met.

1. Age between 22 and 75 years old
2. Severe or moderately severe acute necrotizing pancreatitis, defined per the 2012 Revised Atlanta Classification
3. WON resulting from necrotizing pancreatitis per contrast-enhanced CT with the following characteristics, per the 2012 Revised Atlanta Classification: 
  - Heterogeneous with liquid and non-liquid density with varying degrees of loculations (some may appear homogeneous)
  - Well defined wall
  - Location-intrapancreatic and/or extrapancreatic
4. Infected WON or symptomatic sterile WON

*Note: WON-related symptoms may include: pain, fever, leukocytosis, failure to thrive or deterioration of overall health score, gastric outlet obstruction (GOO), weight loss, biliary obstructive symptoms, systemic inflammatory response syndrome (SIRS), deteriorating organ function, chronic nausea, lethargy, and inability to eat or gain weight*
5. Imaging suggestive of greater than 30% necrotic material
6. WON  $\geq$  6cm in size
7. Eligible for endoscopic intervention
8. Acceptable candidate for endoscopic transluminal drainage
9. Patient understands the study requirements and the treatment procedures and provides written Informed Consent
10. Patient is willing to comply with all specified follow-up evaluations, including willingness to undergo a pre/post CT imaging study

### **5.2 Exclusion Criteria**

Subjects who meet any one of the following criteria will be excluded from this clinical study.

1. Pseudocyst
2. Cystic neoplasm
3. Untreated Pseudoaneurysm  $>$  1cm within the WON
4. More than one WON clearly separated and requiring drainage

5. WONs that require dual modality interventions (endoscopic and percutaneous) from the beginning (i.e. deep paracolic space involvement that is inaccessible through the central drainage access)
6. Prior surgical, interventional radiology or endoscopic procedures for the treatment of the WON
7. Abnormal coagulation:
  - INR > 1.5 and not correctable
  - presence of a bleeding disorder
  - platelets < 50,000/mm^3
8. Intervening gastric varices or unavoidable blood vessels within the access tract (visible using endoscopy or endoscopic ultrasound)
9. WON that poorly approximates the GI lumen ( $\geq 1$ cm away)
10. Pericolic gutter necrosis
11. Pelvic necrosis
12. Prior true anaphylactic reaction to contrast agents, nitinol (nickel titanium), silicone or any other materials contacting the patient
13. Female of childbearing potential with a positive pregnancy test prior to the procedure or intends to become pregnant during the study
14. Currently participating in another investigational drug or device study that has not completed the primary endpoint or that clinically interferes with the endpoints of this study

### **5.3 Point of Enrollment**

A subject is considered “enrolled” after signing the study-specific Informed Consent Form (ICF). Subjects who sign the ICF but subsequently do not meet one or more of the selection criteria will be considered screen failures and excluded from the study.

### **5.4 Withdrawal**

All subjects enrolled in the clinical study (including those withdrawn from the clinical study or lost to follow-up) shall be accounted for and documented. If a subject withdraws from the clinical investigation, the reason(s) shall be reported. If such withdrawal is due to problems related to investigational device safety or performance, the investigator shall ask for the subject’s permission to follow his/her status/condition outside of the clinical study.

Reasons for withdrawal include physician discretion, subject choice to withdraw consent, loss to follow-up and death. While study withdrawal is discouraged, subjects may withdraw from the study at any time, with or without reason, and without prejudice to further treatment. All applicable case report forms up to the point of subject withdrawal must be completed. Additional data may no longer be collected after the point at which a subject has been withdrawn from the study or withdraws his/her consent, for whatever reason. All open

adverse events should be closed or include resolution status. Data collected up to the point of subject withdrawal may be used. Withdrawn subjects will not be replaced. Subjects who withdraw from the study with the study stent in place will be followed per standard of care at the local institution.

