*Note: Removal of stent by 60 days is required if WON not resolved. Patients with unsuccessful or incomplete WON resolution by 60 days will proceed to standard of care treatment outside of this protocol after removal of the AXIOS™ stent; however, the patient outcome will continue to be followed. Alternative interventions may include surgery, endoscopic drainage with double pigtail plastic stents, percutaneous catheter drainage and necrosectomy (video-assisted retroperitoneal debridement (VARD), or endoscopic transluminal debridement, or open necrosectomy).*

- Adverse event assessment/device event assessment
- Organ failure assessment (Marshal scoring system)
- Quality of Life (SF-12)
- Current medication

7 Day (+/-3 days) Post Stent Removal Visit – (Office or phone call):

- Adverse Event assessment
- Current medication

WON Recurrence Assessment Visit/End of Study – at 6 Months (+/- 14 days) from stent removal:

- Recurrence assessment (presence of clinical symptoms and further diagnosis per standard of care (e.g. labs and imaging))
- Adverse Events assessment
- Quality of Life (SF-12)
- Current medication

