#### Statistical Methods:

The primary safety endpoint will be summarized as the proportion of patients who have AXIOS™ stent related or WON drainage procedure related serious adverse events out of all patients who have an AXIOS stent successfully implanted. A Clopper-Pearson exact 95% confidence interval will also be calculated.

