#### Safety Endpoint Success Criteria

An observed rate of 17.5% or lower for the proportion of AXIOS patients with AXIOS™ stent related or WON drainage procedure related serious adverse events is required for success.

This rate is similar to the point estimate of the random-effect meta-analysis of AXIOS stent related or WON drainage related serious adverse events provided in Table 7.2. Note that in the recent systematic review and meta-analysis [28] (Appendix I in Section 21) the complication rates that showed statistically significant differences between plastic stents and LAMS for drainage of WONs were bleeding and stent occlusion, both in favor of LAMS. These findings are particularly important given that (a) bleeding is the most commonly reported serious adverse event, and (b) stent occlusion almost always requires reintervention. It should also be noted that of the plastic stent WON drainage references provided above, even the one reporting the highest complication rates, namely Smoczynski et al [5] conclude that the benefits outweigh the risks: *“In a large group of selected patients with symptomatic walled-off necrosis, endoscopic drainage enables high success rate with acceptable complication rate and low procedure-related mortality.”* Thus the proposed success criteria for safety seems reasonable and acceptable.

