**Table 15.4-1: Investigator Reporting Requirements**

Event Classification	Communication Method	Communication Timeline (Pre-Market Studies) (MEDDEV 2.7/3 ): CLINICAL INVESTIGATIONS: SERIOUS ADVERSE EVENT REPORTING UNDER DIRECTIVES 90/385/EEC AND 93/42/EEC)
Unanticipated Adverse Device Effect / Unanticipated Serious Adverse Device Effect	Complete AE eCRF page with all available new and updated information.	
 
• Within 1 business day of first becoming aware of the event.
 
• Terminating at the end of the study
 

	Provide all relevant source documentation (de-identified/pseudonymized) for reported event upon request of the sponsor	
 
• At request of sponsor
 

Serious Adverse Event	Complete AE eCRF page with all available new and updated information.	
 
• Within 3 calendar days of first becoming aware of the event or as per local/regional regulations.
 
• Reporting required through the end of the study
 

	Provide all relevant source documentation (de-identified/pseudonymized) for reported event upon request of the sponsor	
 
• At request of sponsor
 

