#### ***17.4 Criteria for Suspending/Terminating a Study Center***

Boston Scientific reserves the right to stop the inclusion of subjects at a study center at any time after the study initiation visit if no subjects have been enrolled for a period beyond 12 months after center initiation, or if the center has multiple or severe protocol violations/noncompliance without justification and/or fails to follow remedial actions.

In the event of termination of site participation, all study devices and testing equipment, as applicable, will be returned to BSC unless this action would jeopardize the rights, safety or well-being of the subjects. The IRB/EC and regulatory authorities, as applicable, should be notified. All subjects enrolled in the study at the center will continue to be followed for the protocol follow-up period after study termination. The Principal Investigator at the center must make provision for these follow-up visits unless BSC notifies the investigational center otherwise.

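### Section 5.4 stops data collection for patients the physician withdraws as well as for those who revoke consent, so a later first related SAE would, on its plain reading, count as no event in the primary safety rate

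*Protocol*

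**What the plan says.** Protocol Section 5.4 gives the routes out of the study: "Reasons for withdrawal include physician discretion, subject choice to withdraw consent, loss to follow-up and death". One rule then covers them all, whatever the reason: "Additional data may no longer be collected after the point at which a subject has been withdrawn from the study or withdraws his/her consent". What was gathered before that point is kept: "Data collected up to the point of subject withdrawal may be used". Open adverse events are closed or given a status, and withdrawn patients are not replaced.

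Section 5.4 has two further provisions. If the withdrawal stems from device safety or performance, the investigator asks permission to follow the patient outside the study. A patient who leaves with the stent in place is followed under local standard of care.

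The primary safety proportion (Protocol Section 7.2, SAP Section 3.2.2) is taken "out of all patients who have an AXIOS stent successfully implanted". The treated cohort is the primary analysis cohort in both documents. The success limit in Protocol Section 7.3 is: "An observed rate of 17.5% or lower for the proportion of AXIOS patients".

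Two other places bear on recording. Protocol Section 15.1 requires protocol-reportable events in enrolled patients to be entered in the eCRF, including events after the procedure. For serious adverse events, Table 15.4-1 adds: "Reporting required through the end of the study". Neither mentions withdrawn patients.

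**The concern.** Revoked consent is a good reason to stop collecting data. A physician's decision about a patient who still consents is not, yet 5.4 treats the two alike. Follow-up runs through up to 60 days of stent indwell and then 6 months after removal, so there is time for a first related event after a withdrawal.

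Such a patient stays in the denominator and cannot enter the numerator. For the primary safety rate the error therefore runs one way, towards meeting the limit. Neither document plans an analysis that would reveal it.

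**Working it through.** **Reading the texts together**

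- Section 5.4 addresses withdrawn patients specifically and ends collection for them. Section 15.1 and Table 15.4-1 are general recording rules that are silent on withdrawal. The more specific text would normally govern, but the documents do not say so. This is an unresolved conflict whose plain reading is that collection stops.
- The two follow-up provisions in 5.4 do not feed the endpoint. One is outside the study; the other is routine care.
- No evaluability or missing-data rule in either document removes the patient from the denominator or assigns an outcome.
- The protocol separates stopping treatment from stopping follow-up elsewhere. For collections unresolved at day 60 (Section 6.3), treatment moves to standard of care; "however, the patient outcome will continue to be followed". For a closed site (Section 17.4): "All subjects enrolled in the study at the center will continue to be followed for the protocol follow-up period after study termination".

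**The plan's own figures**

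- The 17.5% limit rests on the meta-analytic rate in Table 7.2. A DerSimonian-Laird random-effects fit on the logit scale to 11/53, 10/81, 29/112 and 5/60 gives 16.67% (10.06% to 26.34%), matching the stated 16.7% (10.1% to 26.3%).
- With 40 patients, 7/40 = 17.5% passes and 8/40 = 20.0% fails.
- With complete data, P(X ≤ 7), X ~ Bin(40, p), is 95.8% at p = 10% (the expected rate), 65.1% at 16.7% and 43.7% at 20%.

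**Chance that an uncounted event turns a fail into a pass**

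Assumed inputs, not in the documents: w = number of consenting patients withdrawn by the physician with no related SAE so far (1 or 2); f = share of the overall risk still ahead of them (0.1 to 1).

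- Counted events: C ~ Bin(40 − w, p). Uncounted events: M ~ Bin(w, r), with r = f × p.
- Flip = P(C ≤ 7 and C + M ≥ 8).
- For w = 1 this is P(C = 7) × r.
- For w = 2 it is P(C = 7) × [1 − (1 − r)²] + P(C = 6) × r².

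Worked case, w = 2, f = 0.5, p = 16.7%: r = 0.0835, P(C = 7) = 0.1585, P(C = 6) = 0.1730. Flip = 0.1585 × 0.1600 + 0.1730 × 0.0070 = 0.0266.

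| True rate | w | f = 0.1 | f = 0.25 | f = 0.5 | f = 1 |
|---|---|---|---|---|---|
| 10% | 1 | 0.05% | 0.13% | 0.26% | 0.53% |
| 10% | 2 | 0.10% | 0.24% | 0.49% | 1.01% |
| 16.7% | 1 | 0.27% | 0.67% | 1.34% | 2.69% |
| 16.7% | 2 | 0.53% | 1.33% | 2.66% | 5.33% |
| 20% | 1 | 0.31% | 0.78% | 1.56% | 3.12% |
| 20% | 2 | 0.64% | 1.60% | 3.18% | 6.32% |

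The mean understatement of the rate is w × f × p / 40. At p = 16.7% and f = 0.5 it is 0.21 percentage points with one such patient and 0.42 with two.

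**The case against.** The strongest reply is that the affected group may be empty. A patient must have a stent implanted, still consent, be withdrawn by the physician, be free of a related SAE so far, and then have a first one before follow-up ends. Exits before implantation never enter the treated cohort. Treatment failure at day 60, the main foreseeable decision point, is not a withdrawal. Withdrawal is discouraged, reasons must be reported, and SAP Section 5.6.3 tabulates disposition by visit. All of this stands. It limits the size of the problem and makes such patients visible, but it does not recover a later event.

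A second reply is that Section 15.1 and Table 15.4-1 already require the event to be recorded. This also has force. A reader might infer that a later SAE is certain to be lost, and the documents do not support that: a site could reasonably follow the recording rules instead. They do not settle which text governs.

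A third reply is that 5.4 does provide for withdrawn patients. It would be wrong to infer that they are abandoned; clinical follow-up exists. It simply does not reach the endpoint.

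A reader might also infer that withdrawals flatter the device throughout. The point is confined to safety. For effectiveness, a withdrawn patient whose collection has not resolved stays in the denominator as a non-success, which works against the device.

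**Conclusion.** The point holds as a minor one. Section 5.4 bars further data for consenting, physician-withdrawn patients and conflicts with the recording rules. With every implanted patient in the denominator and no missing-data rule, the plain reading counts a later first related SAE as no event. Any resulting bias in the safety rate favours the device, at a limit decided by one patient.

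The size is probably small. With one or two such patients and f no more than 0.5, the chance of a changed verdict is at most about 0.5% at a true rate of 10%, 2.7% at 16.7% and 3.2% at 20%. Both w and f are assumptions, and w may be zero. It is tempting to cite the table's upper ends (5.3% and 6.3%), but these need two such patients with all their risk still ahead, although stent placement, itself part of that risk, is already behind them. The documents give no ground for expecting that, nor for calling the safety conclusion unreliable.

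**What to change.** Amend Section 5.4 so that the bar on further data applies only when a patient withdraws consent; loss to follow-up and death end collection in practice. Physician discretion can remain a reason to stop study treatment or procedures. For physician-withdrawn patients who still consent, keep recording SAEs with relatedness, stent removal and the 6-month outcome at the visits already scheduled, and include these data in the primary safety analysis. State that Section 15.1 and Table 15.4-1 apply to them.

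The cost is a protocol amendment with the approvals that Section 9 requires, possibly a consent-form revision, and slight added follow-up for what is likely to be very few patients. No new visits are needed, and the right to revoke consent is unchanged.
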